1. * Provide a detailed description of all research activities (including screening and follow-up procedures) that will be performed for the purpose of this research study. This description of activities should be complete and of sufficient detail to permit an assessment of associated risks. Patients will be recruited from the UPMC Neurosurgery Clinic. The primary surgeon will identify patients who would be eligible for inclusion, ask them if they would be interested in participating, and if so, the enrollment and consent process would be initiated. The participating neurosurgeon is [name], who has agreed to allow us access to his patients. Informed consent will be performed by [name], or the Pl. Enrollment will be performed by the study coordinator and/or trained representative from the Acute Interventional Perioperative Pain Service (AIPPS). Enrollment will include review of eligibility, and detailed explanation of the study.

Screening Visit: Approximately 1 hour

After patients are enrolled into the study at the preoperative neurosurgery clinic, a number of forms will filled out by the subjects: McGill Pain questionaire-Short form (measures pain), pain medication review form, and the Pain Catastrophizing Scale (PCS) (assesses patient's ability to tolerate pain) PROMIS Emotional Distress-Anxiety Short Form (measures anxiety) and PROMIS Emotional Distress-Depression Short Form (measures depression), Brief Psychiatric Rating Scale (assesses psychiatric state of patient) and Neuro-QoL Short Form v1.1 - Satisfaction with Social Roles and Activities (assesses depression/anxiety when it comes to social roles) will also be completed.

Pre-Operative Visit: Approximately 1.5 hrs

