The subject will be asked to come into the [name] on a date after the clinic visit but before their day of surgery for a Pre-Operative Visit. Investigators will work with the subject to determine their opioid dose regimen, and the subject will be asked to come into the Aiken Medical Building thirty minutes before their opioid dose is due and will be asked to bring with them their upcoming dose of pain medication. Prior to taking their pain medication, the subject will then be administered a coldpressor pain sensitivity test. For this test, the subject will place their nondominant hand in a bowl of ice water up to the wrist. Pain threshold is defined as the time in seconds that is takes for the subject to first report the sensation of pain in the immersed hand. Pain tolerance is defined as the time in seconds that it takes for the subject to withdraw their hand from the ice water because it has become too uncomfortable for them to keep their hand immersed any longer. A cut-off of four minutes will be imposed to limit the potential for any tissue damage. At this time, the subject will be asked to remove their hand from the ice water, even if they say that they could keep their hand immersed for longer. Pain threshold, tolerance and cut-off will be recorded using a stop watch. Heart rate and blood pressure

will be recorded before and after the cold-pressor test. Once the cold pressor test is completed, the McGill Pain Questionnaire will be administered. After this questionnaire is complete, the subject will take the dose of opioid medication they have brought from home and are scheduled to receive and will wait in the clinic for 30 minutes for the pain medication to take effect. Once the 30 minutes is complete, the cold-pressor test will be repeated, heart rate and blood pressure collected before and after, and McGill Pain Questionnaire will be administered again. Opioid-analgesic efficacy will be estimated by the change in pain threshold and tolerance observed after the opioid was consumed relative to initial assessment of pain threshold and tolerance. The subject will be compensated \$50 for this pre-operative visit.

Surgical Visit:

Study groups:

Patients will be randomized to one of the following groups:

- 1. Intraoperative ketamine- post operative 48 hr ketamine infusion
- 2. Intraoperative placebo (saline)- post operative placebo (saline) infusion

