6-Week Follow-Up Visit: Approximately 1.5 hours

The subject will be asked to come to the [name] approximately 6 weeks after their surgery for a 6-Week Follow-Up Visit. Investigators will work with the subject to determine their post-operative opioid dose regimen, and the subject will be asked to come in for the visit thirty minutes before their opioid dose is due and bring with them their upcoming dose of pain medication. Prior to taking their pain medication, the subject will then be administered a cold-pressor pain sensitivity test, in a manner identical to that use during the pre-operative assessment.In addition to the McGill Pain Questionnaire-Short form, a pain medication review form, the Pain Catastrophizing Scale (PCS) (Sullivan, 1995), the PROMIS Emotional Distress-Anxiety Short Form, the PROMIS Emotional Distress-Depression Short Form, Brief Psychiatric Rating Scale and Neuro-QoL Short Form v1.1 - Satisfaction with Social Roles and Activities will also be completed. The subject will be compensated \$50 for this 6-week follow-up visit.

Upload a copy of all materials used to collect data about subjects: (Attach all surveys, interview/focus group scripts, and data collection forms except for case report forms, SCID or KSADS):

	Document	Category	Date Modified	Document History
View	Brief Psychiatric Rating Scale (0.01)	Data Collection	3/6/2019	History
View	PROMIS v1.0 ED-Depression Short Form 1.pdf(0.01)	Data Collection	3/6/2019	History
View	PROMIS v1.0 ED-Anxiety Short Form 1.pdf(0.01)	Data Collection	3/6/2019	History
View	Pain%20catastrophizing%20scale-1.docx(0.01)	Data Collection	3/6/2019	History
View	Neuro-QOLv1.1- SatisfactionwithSocialRolesandActivitiesSF 03-06- 2014.pdf(0.01)	Data Collection	3/6/2019	History
View	Medications- questionaire.doc(0.01)	Data Collection	3/6/2019	History
View	Mcgill pain questionaire.docx(0.01)	Data Collection	3/6/2019	History

3. * Will blood samples be obtained for research purposes?

○ Yes [©] No

View: Pitt SF: Consent Process

Consent Process

Enter N/A in response to the following questions if a Waiver of Consent is requested for all research activities or if no subjects are being enrolled.

1. * Indicate where the consent process will take place and at what point consent will be obtained:

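### At 6 weeks, opioid analgesic efficacy is the response to a dose set after randomisation and exists only for patients still taking opioids, so an arm difference cannot be read as evidence on tolerance

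*Protocol*

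**What the plan says.** - **Status.** Protocol, Study Design, item 3 puts opioid analgesic efficacy, before and after surgery, under the primary outcome. The cold pressor test is also listed there as a secondary outcome.
- **Definition.** Protocol, Research Activities, item 1 (Pre-Operative Visit): "Opioid-analgesic efficacy will be estimated by the change in pain threshold and tolerance observed after the opioid was consumed relative to initial assessment". The opioid is the patient's own scheduled dose, brought from home. The test is done before it and again after a wait: "Once the 30 minutes is complete, the cold-pressor test will be repeated". A four-minute limit applies.
- **6-week visit.** Same item: investigators establish the post-operative regimen, and the patient comes "thirty minutes before their opioid dose is due and bring with them their upcoming dose of pain medication". The pre-dose test is done "in a manner identical to that use during the pre-operative assessment". The post-dose repeat is not written out. The paperwork includes the "McGill Pain Questionnaire-Short form, a pain medication review form". No such form is listed at the pre-operative cold-pressor visit.
- **Expected effect on opioid use.** Study Aims, item 1 hypothesises lower postoperative consumption under ketamine. Item 2 predicts a long-term effect on opioid use.
- **Entry.** Study Design, item 5 requires daily opioid use for at least 2 months at 60 mg/day or more of oral morphine equivalent. Nothing requires a dose at 6 weeks.
- **Analysis.** The SAP, like Study Design, item 8, offers mainly descriptive statistics and a possible two-sample t test.

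**The concern.** The outcome's name, and the rationale in Study Aims, item 2 (tolerance that depends on the NMDA receptor), invite a reader to treat an arm difference as evidence on how well opioids work after ketamine. As measured at 6 weeks, it is the response to whatever dose the patient then takes. If ketamine lowers opioid use, the ketamine arm may be tested at smaller doses. A smaller change could then mean a smaller dose, and no difference could hide a gain in response per mg.

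The second problem is who has a score. A patient who has come off opioids, arguably a good result, has no post-dose change. Neither document says how such patients are handled, and the t test would run on those who remain, a group selected by something that happens after randomisation. The pilot is meant to inform a larger trial, so a misreading here would carry forward.

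**Working it through.** The documents give no effect size, SD, power or stopping rate, so there is no figure to reproduce. The finding rests on the text; the numbers only give scale.

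**1. Is the post-dose repeat intended at 6 weeks?** Probably. The patient is asked to bring the dose, the test is to match the pre-operative one, efficacy is listed as post-surgical too, and the visit lengths agree: "Pre-Operative Visit: Approximately 1.5 hrs" and "6-Week Follow-Up Visit: Approximately 1.5 hours".

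**2. How the dose enters (illustration).** Assume 60 mg/day (the entry level) in four equal doses: 60/4 = 15 mg. If daily use halves to 30 mg, the next dose could be 30/2 = 15, 30/3 = 10 or 30/4 = 7.5 mg. Assume the same dose-response curve in both arms:

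| Test dose | Ratio to 15 mg, proportional response | Ratio, Emax curve with ED50 = 15 mg |
|---|---|---|
| 15 mg | 1.00 | 1.00 |
| 10 mg | 0.67 | (10/25)/(15/30) = 0.80 |
| 7.5 mg | 0.50 | (7.5/22.5)/(15/30) = 0.67 |

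The same fall in daily use gives apparent ratios from 1.00 to 0.50 with identical responsiveness. Under proportional response, gains per mg of 0%, 50% or 100% (1/ratio − 1) would show as no difference. Daily totals therefore cannot settle the reading; the test dose is needed.

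**3. How leaving out patients enters (illustration).** Twenty patients at 1:1 gives 10 per arm. Assume a standard normal response and m patients missing from one arm.

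| | m = 1 | m = 2 | m = 3 |
|---|---|---|---|
| Extreme bound: the m highest (or m lowest) responders missing, mean shift (simulation, 400,000 arms) | 0.171 SD | 0.318 SD | 0.457 SD |
| Stopping correlated 0.3 with response (0.3 × bound) | 0.05 | 0.10 | 0.14 |
| Stopping correlated 0.5 (0.5 × bound) | 0.09 | 0.16 | 0.23 |
| Unrelated: mean 0, SD = sqrt(1/(10 − m) − 1/10) | 0.105 | 0.158 | 0.207 |

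**4. Scale.** 95% CI half-width at 10 per arm: t(18) × sqrt(2/10) = 2.101 × 0.447 = 0.94 SD. With 1, 2 or 3 missing from one arm it is 0.97, 1.01 or 1.05 SD. The largest shift under the assumed correlations is 0.23/0.94, about a quarter of the half-width.

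**5. Precision of the comparison proposed below.** With all 20 tested, no times at the cut-off and baseline correlation r (assumed), the half-width is about t(17) × sqrt(2/10) × sqrt(1 + 1/16) × sqrt(1 − r²) = 0.973 × sqrt(1 − r²). The term 1/16 allows for chance baseline imbalance. This gives 0.84 SD at r = 0.5 and 0.70 SD at r = 0.7. Below r of about 0.26 it is slightly wider than the unadjusted 0.94.

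**The case against.** The case for leaving the plan alone has weight.

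- **The documents do not claim dose-for-dose efficacy.** Correct. If every randomised patient has a score, the contrast is a valid effect of assignment on response to the current dose. Only the reading as responsiveness fails.
- **It is a 20-patient, mainly descriptive pilot, and the shifts are small beside the interval.** Also correct. A reader might infer a large bias, or one against ketamine; neither is supported. Ketamine could raise response per mg while lowering the dose, so even the net direction is open. But a descriptive table still has to say what was measured, at what dose and in whom.
- **Dose capture is partly in place.** Investigators establish the regimen at both cold-pressor visits, and 6-week use in morphine equivalents is already an outcome. The form's content is not shown, so it may hold the test dose. What is missing is a stated link between that dose and this outcome.
- **Patients off opioids might be thought to have no 6-week visit.** The text does not support that. The visit is set at about 6 weeks after surgery, with questionnaires also due; the dose only fixes the hour of arrival.
- **The early hand-withdrawal advice in Risk and Benefits, item 2 might seem to undo the tolerance measure.** It applies only to particularly sensitive subjects. Reconciling it with the tolerance definition is a separate, minor point. So is the different primary outcome in Basic Information, item 3 (PCA use over 72 hours).

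**Conclusion.** The concern holds as a matter of interpretation and of an outcome left undefined for some patients. The 6-week change score mixes test dose with opioid responsiveness and cannot be read as evidence on tolerance. Once any patient has stopped opioids, a comparison of those with a score is not a randomised comparison.

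The size and direction of any distortion are unknown, because the stopping rate, the dose-response shape and the link between stopping and response are not given. On the assumptions shown (10 per arm, 1 to 3 missing from one arm, correlation 0.3 to 0.5), the average shift is about 0.05 to 0.23 SD against a half-width of 0.94 SD; if stopping is unrelated to response, the expected shift is zero. These figures also assume an unbounded normal response, although times are capped at four minutes. It would be wrong to say that the documents omit the 6-week repeat test: it is implied, and only needs stating. The change is worth making because it costs little and makes a listed primary outcome readable.

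**What to change.** Keep the outcome and make four changes.

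1. In the 6-Week Follow-Up Visit text, state that the wait and post-dose repeat are done for patients with a scheduled dose, and that patients off opioids still have the single cold-pressor test.
2. Record the drug and amount taken at each cold-pressor test in oral morphine equivalents, on the existing form if it allows, and report it by arm beside the change. Adjusting for the 6-week dose is no substitute: it is set after randomisation, so adjustment would not restore a randomised comparison.
3. Use one label: response to the patient's current dose, among patients who took a dose. Report it descriptively, and read it as an effect of assignment only if every randomised patient has a value. Give by arm the numbers tested, refused and without a dose. Do not score the last group as zero; with 10 per arm, 1, 2 or 3 zeros would multiply the arm mean by 0.9, 0.8 or 0.7.
4. Under the existing cold pressor secondary outcome, compare 6-week pre-dose threshold and tolerance between arms in all tested patients, adjusted for the pre-operative pre-dose value, with a 95% CI. Label it pain sensitivity; it may reflect current opioid exposure and answers a different question. The protocol already says "Pain threshold, tolerance and cut-off will be recorded using a stop watch", so report how many times reach the four-minute limit. A censored model is optional.

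Cost: at most one data item, a few table rows, one added comparison and a more cautious reading of the change score. No new visit is needed. The added comparison still does not cover patients who refuse the test.

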Randomization will occur by a computer based system at a 1:1 ratio. The Investigational Drug Pharmacy will create the randomization log and IDS will randomize the subject independent of the research team. The study drug/placebo will look identical to maintain the blind for all clinicians and research staff involved.

At the day of surgery, subjects will be seen by team members of the Acute Interventional Perioperative Pain Service preoperatively. Pregnancy will be assessed via medical record, as it is standard of care for these patients to take a pregnancy test day of surgery. Since the ketamine infusion will occur for 48 hours while patient is in the hospital, there is little risk of becoming pregnant during study drug treatment period

Enrolled participants will receive a 1 mg/kg dose of intravenous ketamine or saline 15 minutes after induction of general anesthesia. Thereafter, a continuous infusion of 0.20 mg/kg/hr ketamine or saline with a maximum dose of 20 mg/hr will be run to conclude at 48 hours after the end of the surgery (fascial closure).

A standardized general anesthesia protocol will be used by the hands-on provider. All drugs used intraoperatively, including total hydromorphone dose, will be collected from the electronic medical record.

The amount of narcotics and non-narcotic analgesics administered in the operative and postoperative period will be collected from the electronic chart from day of surgery until discharge. VAS pain scores will be collected

from the PACU until discharge from the hospital.

Pain will be monitored every four hours, except during the night when the participant is asleep. We will use a scale from 0-10, 0 being no pain, 5 being moderate pain and 10 being the worst imaginable pain. The participant will also be asked to score pain at its best and worst over the period since they were last asked.

Post-Op Visit: Approximately 1 hour

Patients will follow-up at Neurosurgery clinic at 10-14 days postoperatively. At this time daily opioid usage will be assessed and converted to morphine equivalents/24 hr. At this visit, the McGill Pain questionnaire-Short form, pain medication review form, and the Pain Catastrophizing Scale (PCS) (Sullivan, 1995). PROMIS Emotional Distress-Anxiety Short Form and PROMIS Emotional Distress-Depression Short Form, Brief Psychiatric Rating Scale and Neuro-QoL Short Form v1.1 - Satisfaction with Social Roles and Activities will also be completed by the participant.

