Patients will be recruited from the UPMC Neurosurgery Clinic. The primary surgeon will identify patients who would be eligible for inclusion, ask them if they would be interested in participating, and if so, the enrollment and consent process would be initiated. Participating neurosurgeons include Drs. [name], who will identify eligible patients. Informed consent will be performed by this Neurosurgeon, the PI, or other co-investigator in the study. Enrollment will be performed by the study coordinator and/or trained representative from the Acute Interventional Perioperative Pain Service

(AIPPS). Enrollment will include review of eligibility, and detailed explanation of the study.

- 2. * Describe the steps that will be taken to minimize coercion and undue influence, including assurance that there is sufficient time for subjects to make an informed decision:
 - In order to minimize the possiblity of coercion or undue influence, the patients will be first informed that the choice of participation in the study is totally voluntarily in nature, and they will receive a standard of care when they decide not to participate in the study. Prospective patients will be encouraged to ask questions and to discuss the study with others during the consent process. Then, they will be assured that after participation in the study, they will receive either ketamine or placebo in a randomized fashion if they participate in the study. Informed consent will occur in the neurosurgery clinic during their pre-surgical clinic visit.
- 3. For studies that involve multiple visits, describe the process to ensure ongoing consent:

At each visit, the subjects will be asked if they have any questions and will be reminded about the goals and objectives of the study. The subjects will also be reminded that they can withdraw from the study at any time.

- 4. * Steps to be taken to ensure the subjects' understanding:
 Individuals will be provided with full explanation of study-related goals and procedures. Questions will be answered from the patient as well as their family members as necessary. Patients will be given as much time as necessary to read the consent form and ask questions.
- 5. * Are you requesting an exception to the IRB policy related to the informed consent process:

○ Yes No

View: Pitt SF: Consent Forms

Consent Forms

1. Consent Forms:

ı	Document	Category	Date Modified	Document History
View	Consent draft_Version 4.3.19.docx(0.03)	Consent Form	4/3/2019	History

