privilege, whenever possible identifiers will be removed from study-related information, patients' computer medical information will only be available through password access.

Identifiable data will be kept in a single encrypted file on the shared (z:) drive behind the UPMC firewall. All other study-related data (such as paper records and data for analysis) will have all identifiers removed.

View: Pitt SF: Risk and Benefits

Risk and Benefits

1. * Enter all reasonably foreseeable risks, discomforts, hazards, or inconveniences to the subjects related to subjects' participation in the research:

	Research Activity	low dose ketamine infusion
	Other Risks	No Value Entered
VICW	Infrequent Risks	feelings of frustration, embarrassment or boredom
View	Common Risks	No Value Entered
	Research Activity	completion of questionnaires
	Other Risks	No Value Entered
VIOW	Infrequent Risks	Breach of confidentiality
View	Common Risks	No Value Entered
	Research Activity	Collection of information from medical records

Common Risks

No Value Entered

Allergic Reaction (rare) Blurred vision(infrequent) Confusion (infrequent) Drowsiness (infrequent) Increased or decreased blood pressure or heart rate (infrequent) Mental or mood changes (infrequent) Nausea and vomiting (infrequent) Dreams, hallucinations and delirium (infrequent) Liver injury (rare)

Other Risks

With respect to the risk of liver injury, there have been reports of reversible, elevated liver enzymes associated with long term, repetitive use of high dose ketamine, although there are currently no reports of liver injury associate with low dose ketamine, which is used in this study. That being said, you are instructed to notice the following signs and symptoms of liver injury, and

View

	report to physicians with the information of previous exposure of ketamine infusion: • Discolored skin and eyes that appear yellowish • Abdominal pain and swelling • Itchy skin that doesn't seem to go away • Dark urine color • Pale stool color • Bloody or tar-colored stool • Chronic fatigue • Nausea • Loss of appetite
--	---

View	Research Activity	cold pressor test
	Common Risks	No Value Entered
	Infrequent Risks	Excessive painful sensation (rare) tissue damage (rare)
	Other Risks	No Value Entered

2. * Describe the steps that will be taken to prevent or to minimize risks: Experimental Interventions:

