Participants will receive ketamine infusion at the in-patient units. Should any complications associated with the medication occur, emergency cart is readily available at the units. Acute Interventional Perioperative Pain Service (AIPPS), which is responsible for the participants' postoperative pain management, is 24/7 available to address any associated issues.

All aspects of patients' analgesic care, including the management of low-dose ketamine infusion, will be administered under the consultation of the acute Interventional Perioperative Pain Service, which routinely uses these infusions in the managment of perioperative pain in opioid dependent or difficult to treat patients. This service is on call 24 hours/day. Ketamine infusions will only be administered to inpatients who are on floors where nursing staff has undergone training in the managment and administration of low dose ketamine infusions.

Patients will be instructed to notice the signs and symptoms of liver injury and report to medical staff about previous exposure to ketamine infusion. Patients will also be followed up for mental status change with Brief Psychiatric Rating Scale.

If the subject is particularly sensitive to the cold pressor test, they will be encouraged to move hand from the ice as soon as they feel any pain sensation. There is a four-minute limit on the test to reduce any risk of tissue damage. The participant will be made aware that they can refuse the cold pressor test should they choose.

Investigators who will access the identifiable medical records already have normal clinical access to all necessary records, as granted by the privacy office for job-related needs. Thus, only HIPAA trained research staff will be handling this information and this information will be stored in a locked

database protected by the UPMC firewall. Additionally, all data generated under this protocol will be monitored and maintained by the principal investigator. Any databases that contain identifiable information will be stored on a departmental drive on the UPMC network created for the principal investigator, and all data will be deidentified according to the HIPPA "safe harbor" guidelines prior to statistical analysis.

Pregnancy is being assessed via a medical record review. Since the ketamine infusion will occur for 48 hours while patient is in the hospital, there is little risk of becoming pregnant during study drug treatment period.

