The follow up contact will be made by trained physicians.

Financial ris	sks - will the subject or insurer be charged for any research
required pro	ocedures?
○ Yes ⊙	No

- 4. Describe the steps that will be taken to protect subjects' privacy:
 Research intervention will be conducted in a private room with the patient,
 collected information will be limited to that which is necessary for the goals
 of the research study, access to the patient's private information will be
 limited to those involved in the patient's medical care.
- 5. What steps will be taken in the event that a clinically significant, unexpected disease or condition is identified during the conduct of the study:
 - The patient's primary medical team will be immediately notified of the unexpected, clinically significant condition. The patient's clinically significant medical condition will be managed accordingly. If any of the clinically significant medical condition is related to the study, then the patient's participation in the study will be re-evaluated, with the possibility of the patient being withdrawn from the study if this leads to the resolution of the clinically significant medical condition
- 6. Describe the potential benefit that individual subjects may experience from taking part in the research or indicate if there is no direct benefit. Do not include benefits to society or others:
 Patients with chronic pain and opioid dependence may experience better analgesia in the postoperative period. There is no guaranteed direct benefit to participants.
- 7. Do you anticipate any circumstances under which subjects might be withdrawn from the research without their consent?

Ye	s 🖰	No
----	-----	----

- * Describe the circumstances and any procedures for orderly termination: Subject's failure to follow study procedures Severe allergic reaction to study drug
- 8. Describe procedures that will be followed when subjects withdraw from the research, including partial withdrawal from procedures with continued data collection and data already collected:

If a participant withdraws from research, follow up will cease but data previously collected may still be used in analysis.

View: Pitt SF: Placebo Arm

Placebo Arm

- 1. * Is there a commonly used diagnostic/treatment approach that is currently recognized as being effective for the proposed subjects' disease or condition, and that will be withheld from subjects assigned to the placebo arm of this research study:

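### The liver-injury instruction tells every blinded participant to report a ketamine exposure that about half will not have had, and it does not direct liver signs to the study team

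*Protocol*

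**What the plan says.** The instruction appears in two places in the Protocol's Risk and Benefits section. Item 2, on minimizing risk, reads: "Patients will be instructed to notice the signs and symptoms of liver injury and report to medical staff about previous exposure to ketamine infusion". Item 1, in the entry for the low-dose ketamine infusion, lists nine liver signs and tells the reader, addressed as *you*, to "report to physicians with the information of previous exposure of ketamine infusion". The stand-alone risk form near the end of the Protocol repeats that entry, so it is not a third independent statement.

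Research Activities, item 1, sets a 1:1 allocation between ketamine and saline and adds: "The study drug/placebo will look identical to maintain the blind for all clinicians and research staff involved". Consent Process, item 2, says participants will be assured that "they will receive either ketamine or placebo in a randomized fashion if they participate in the study".

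On safety follow-up, Placebo Arm item 6 describes adverse-event monitoring by the research team during the hospital stay. Data Safety and Monitoring item 1 places continuous data monitoring in the period of active in-hospital treatment. After discharge there are two visits, at day 10-14 and at about 6 weeks. The forms listed for the first end with "Brief Psychiatric Rating Scale and Neuro-QoL Short Form v1.1 - Satisfaction with Social Roles and Activities will also be completed by the participant", and the 6-week list is the same, with a cold-pressor test added.

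**The concern.** A safety instruction in a blinded trial should be one that every participant can follow truthfully. This one asks participants to state a drug exposure that they cannot know about and that the saline group did not have. A clinician seeing a saline patient with jaundice or dark urine could be given a wrong drug history and could weigh ketamine as a cause when it was never given.

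The second point is where the information goes. Participants are told to speak to physicians or medical staff. Some of those may be trial co-investigators, but the text does not ask the participant to tell the study team. A participant who saw an outside physician could follow the instruction fully without the trial hearing of the event. That would matter less if the post-discharge visits were described as asking about symptoms in general, but they are not.

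**Working it through.** The Protocol gives no figure to reproduce here. The check is mainly a comparison of texts.

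**Step 1: whom the instruction covers.** Item 2 speaks of patients generally and item 1 addresses the participant directly. Neither limits the instruction to the ketamine arm, and neither says possible exposure, study drug or placebo.

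**Step 2: for whom it is true.** Inputs are 20 participants (Study Design, item 1) and 1:1 allocation (Research Activities, item 1). Expected saline arm: 20 × 1/2 = 10. This is the size of the group for whom the statement is untrue. It is not a forecast of incorrect reports, because the number of saline patients who would develop a listed sign and report it as ketamine exposure is unknown.

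**Step 3: whether it can be read conditionally.** Suppose it means that those who had ketamine should say so. A blinded participant cannot tell whether that applies. Read literally, the instruction is wrong for the saline arm. Read conditionally, no one can follow it.

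**Step 4: where a liver sign would be picked up after discharge.** Each post-discharge visit lists the same seven forms. The Screening Visit text gives the purpose of six of them, and the seventh is a medication review:

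| Form | Purpose as described |
|---|---|
| McGill short form | Pain |
| Pain Catastrophizing Scale | Ability to tolerate pain |
| PROMIS Anxiety | Anxiety |
| PROMIS Depression | Depression |
| Brief Psychiatric Rating Scale | Psychiatric state |
| Neuro-QoL | Social roles |
| Pain medication review | Medication |

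None is described as a general adverse-event or liver-symptom inquiry. Risk and Benefits item 2 gives mental-status change a named follow-up instrument, the Brief Psychiatric Rating Scale. For liver injury it gives only self-report.

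**Step 5: what else could capture it.** Serious adverse events are reportable with no stated hospital limit (Data Safety and Monitoring, item 1). Participants are invited to ask questions at each visit (Consent Process, item 3). Physicians make the follow-up contact (Risk and Benefits, item 2). The coordinator monitors subjects daily, with no stated end (Placebo Arm, item 9). None of these says what is asked about symptoms after discharge. The upload field for data-collection materials excludes case report forms, so an adverse-event log may exist that is not shown.

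**The case against.** The strongest reply is that this is shorthand. The risk entry sits under the ketamine infusion, where the form asks for that drug's risks, and item 2 is written throughout as if describing the active arm. Participants have already been told that they may receive placebo, so a sensible one would say so. The consent form, which carries the operative wording, was not available and may put it better. For a saline patient, a clinician who assumes exposure is at least being cautious. The Protocol calls liver injury rare, cites no reports at low dose, and excludes patients with significant liver disease or exposure to CYP3A or CYP2B6 inhibitors.

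Most of this stands, and it keeps the point small. It does not rescue the wording. The text is an instruction to participants, who cannot apply an active-arm-only reading, and the consent explanation softens the instruction without qualifying it.

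On the visits, it is fair to reply that the statements about in-hospital monitoring do not confine adverse-event collection to the hospital, and that a list of questionnaires cannot show that no inquiry exists. That stands too, so the visit question is offered as an improvement and not as a correction of an error.

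**Conclusion.** The concern holds as a minor one. The instruction does not fit a 1:1 double-blind saline-controlled trial, and it does not direct liver signs to the study team. No endpoint or planned descriptive analysis is affected. The conclusion assumes that the instruction reaches participants in substantially the form the Protocol gives.

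Four stronger readings are tempting, and the documents do not support them:

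- **That about 10 participants would give false histories.** Ten is an arm size. The relevant count depends on liver signs and on what patients then say, and neither is known.
- **That late harms would go unrecorded.** The documents show only that a general symptom inquiry is not described. Several other contacts exist, and the case report forms were not available. The fact that none of seven forms is such an inquiry describes the list and does not measure missed events.
- **That the instruction breaks the blind.** Every participant gets the same wording, so it reveals no allocation.
- **That clinicians could not learn the allocation in an emergency.** No release procedure is described, but the Protocol says: "The Investigational Drug Pharmacy will create the randomization log and IDS will randomize the subject independent of the research team". A holder of the allocation therefore exists. Risk and Benefits item 5 also has the "primary medical team will be immediately notified of the unexpected, clinically significant condition". The absence of a written procedure is missing detail and does not show that the plan is faulty.

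**What to change.** Reword the instruction in Risk and Benefits items 1 and 2, and in the repeated risk form, along these lines: *tell any clinician that you took part in a blinded study and may have received ketamine or saline, and also notify the study team*. Make the same change in the consent form if it uses the same wording. The cost is an edited sentence in each place.

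As a cheap improvement, ask one open adverse-event question, with the listed liver signs as a prompt, at the existing day 10-14 and 6-week visits, unless the case report forms already do so. Ask it after the pain assessments, and at 6 weeks after the cold-pressor test, so that prompting for symptoms does not colour the pain ratings. Summarise the answers as counts by arm, which fits the SAP's mainly descriptive approach. This takes a few minutes at visits already planned. The downside is that 3 of the 9 listed signs (nausea, fatigue and poor appetite) are non-specific and will produce some positive answers needing clinical review.
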